#### Alternatives to Participation

Patients receiving buprenorphine at their primary care site can stay in the regular clinical OBOT program at their individual site and opt to not participate in this research study.

## **5.2 Handling of Study Interventions**

The MTPC manual and the Low-Dose Mindfulness (LDM) manual have been tailored specifically for participants with OUD in primary care buprenorphine treatment. Prior to the start of the R33 M-ROCC groups, the manuals will be finalized based on the remaining participant feedback from the R21 phase, and merged into a single adapted, stage-based Mindful Recovery OUD Care Continuum document with an ascending practice dose ladder, which was demonstrated to result in high levels of daily mindfulness practice among participants with MAT in previous trials. These manuals will be further refined for adaptation to a live-online setting. This manual will be sent to NCCIH prior to start of R33 study enrollment.

## 5.3 Concomitant Interventions

### 5.3.1 Allowed Interventions

All other non-experimental interventions are allowed as long as they do not conflict with inclusion/exclusion criteria. Many participants are also receiving standard care for their chronic illness and mental health, which may include trials of psychopharmacologic agents or psychotherapy.

### 5.3.2 Required Interventions

Participants will be required to remain in their regular OBOT program according to standard of care at their referring site. All BUP prescriptions will be tracked and managed by the participant's clinical team. There are no additional required interventions except the mindfulness practice, which will be encouraged in M-ROCC.

### 5.3.3 Prohibited Interventions

Psychopharmacologic treatments AND diagnoses related to active psychosis, thought disorder, schizophrenia, or schizoaffective disorder as these would indicate that the participant meets one of the exclusion criteria. Psychopharmacologic treatments with atypical antipsychotics and mood stabilizers for the adjunctive treatment of mood disorders or bipolar 2 disorders are NOT prohibited unless there is active psychosis.

## 5.4 Adherence Assessment

### Measurement and Reporting of Participant Accrual, Compliance with Inclusion/Exclusion Criteria:

Review of the rate of participant accrual and compliance with inclusion/exclusion criteria will occur monthly by the data analyst with reports to PI monthly to ensure that a sufficient number of participants are being enrolled. Accrual will be reported twice yearly to the DSMB.

### Measurement and Reporting of Participant Adherence to Intervention Protocol:

Participants will be considered adherent to the intervention protocol if they attend at least 3 LDM or control groups. Participants will be considered adherent to the overall M-ROCC intervention if they attend at least 12 MTPC-OD or MCS groups and were adherent to the LDM group with at least 3 LDM sessions attended. Participants will be considered adherent to the control intervention if they complete 15/24 control groups.

They will be adherent to weekly surveys and eligible for a completion bonus if they complete 75% of these survey sessions and all 2-week time periods have an oral fluid screen. If assigned a study phone, participants must also return this phone to be eligible to receive this bonus.

*Measurement and Reporting of Group Leader Adherence to Intervention Manual:*

Data on adherence to the intervention protocol will be collected weekly by research staff and reviewed monthly by the PI, and twice yearly by the study statistician and DSMB. Adherence of participants will be evaluated by attendance at weekly sessions (Control, LDM, MCS or MTPC-OD). Adherence for each intervention session will be rated on the following scale: 0 = absence; 1 = completed; 2 = incomplete (with comments). An explanation of study staff efforts to monitor and address participant adherence deficits will be documented and reviewed twice weekly by the senior RC. All sessions will be audio recorded, and 10% of recordings will be reviewed by a trained reviewer rating for adherence, competence, and fidelity, using the MBI:TAC.

## 6. STUDY PROCEDURES

### 6.1 Schedule of Evaluations: *Table 1a: Schedule of Evaluation from Screen to Wk 8*

	Consent & Screening	Baseline		Study Week							
			1	2	3	4	5	6	7	8	
Informed Consent and Screening Session											
Informed Consent Form	X										
Consent Quiz	X										
PROMIS-ASF	X									X	
MOCA-BLIND – if required	X										
CAT-MH	X										
PhenX Addiction Core T1	X										
Demographics Survey	X										
Baseline Battery											
Meditation and Mindfulness Experience (SMME)		X									
Adverse Childhood Experiences (ACE)		X									
Clinical Assessments											
PROMIS-PISF		X								X	
Beck Anxiety Inventory (BAI)		X								X	
Oral Fluid Toxicology Results		X				X				X	
Weekly Survey			X	X	X	X	X	X	X	X	
Pain Catastrophizing Scale (PCS)		X								X	
Substance Craving Scale (SUBCS)		X	X	X	X	X	X	X	X	X	
Self-Regulation Battery											
Experiential Avoidance (BEAQ)		X								X	
Difficulty in Emotion Regulation (DERS-16)		X								X	
Perceived Stress Scale (PSS)		X								X	
Self-Compassion Scale (SCS)		X								X	
Interoceptive Awareness (MAIA-2)		X								X	
Nonattachment to Self Scale (NTS)		X								X	
Self-Critical Rumination Scale (SCRS)		X								X	
Experiences Questionnaire Decentering Subscale (EQD)		X								X	
Mechanisms Battery											
Interpersonal Mindfulness Scale		X								X	
Credibility/Expectancy Survey -Stress				X							
Credibility/Expectancy Survey - OUD				X							
Five Facet Mindfulness Questionnaire (FFMQ)		X								X	
Group Attitudes Survey										X	
Monitoring surveys											
Weekly Mindfulness Practice Diary			X	X	X	X	X	X	X	X	

Weekly Recovery Skills Diary			X	X		X	X	X	X	X	X
Adverse Events Reporting Form			X	X		X	X	X	X	X	X
Qualitative Interview											
Duration (min)	69	77	7	13		7	17	7	7	7	76
Payments for Study Visits (\$)	20	40	7	12		7	12	7	12	7	52

**Table 1b: Schedule of evaluations weeks 9-24**

	Study Week																Duration (min)
	9	10	11	12	13	14	15	16	17	18	19	20	21	22	23	24	
Informed Consent and Screening Session																	
Informed Consent Form																	20
Consent Quiz																	10
PROMIS-ASF								X								X	3
MOCA-BLIND – if required																	10
CAT-MH				X												X	12
PhenX Addiction Core T1																	10
Demographics Survey																	4
Baseline Battery																	
SMME																	3
Adverse Childhood Experiences (ACE)																	4
Clinical Assessments																	
PROMIS-PISF								X								X	3
Beck Anxiety Inventory (BAI)								X								X	5
Oral Fluid Toxicology Results				X		X		X		X		X		X		X	10
Weekly Survey	X	X	X	X	X	X	X	X	X	X	X	X	X	X	X	X	1
Pain Catastrophizing Scale (PCS)								X								X	3
Substance Craving Scale (SUBCS)	X	X	X	X	X	X	X	X	X	X	X	X	X	X	X	X	2
Self-Regulation Battery																	
Experiential Avoid (BEAQ)								X								X	3
Emotion Regulation (DERS-16)								X								X	5
Perceived Stress (PSS)								X								X	3
Self-Compassion (SCS)								X								X	5
Interoceptive Awareness (MAIA-2)								X								X	5
Nonattachment to Self Scale (NTS)								X								X	2
Self-Critical Rumination Scale (SCRS)								X								X	3
Experiences Questionnaire Decentering Subscale (EQD)								X								X	5
Mechanisms Battery																	
Interpersonal Mindfulness Scale								X								X	4
Credibility/Expectancy Survey -Stress																	3
Credibility/Expectancy Survey - OUD																	3
Five Facet Mindfulness Questionnaire (FFMQ)								X								X	6
Group attitudes								X								X	2
Monitoring surveys																	
Weekly Mindfulness Practice Diary	X	X	X	X	X	X	X	X	X	X	X	X	X	X	X	X	2
Weekly Recovery Skills Diary	X	X	X	X	X	X	X	X	X	X	X	X	X	X	X	X	2
Adverse Events Form	X	X	X	X	X	X	X	X	X	X	X	X	X	X	X	X	2

Qualitative Interview																	X		60
Visit Duration (min)	7	7	7	31	7	17	7	76	7	17	7	17	7	17	7	98			
Payments for Visits (\$)	7	12	7	12	7	12	7	52	7	2	7	12	7	12	7	102			

## 6.2 Description of Evaluations

### 6.2.1 Screening Evaluation

#### Pre-Screening Process

In order to be eligible to participate in the study, all patients must have an active buprenorphine prescription from a provider and must reside in a state approved by the IRB for recruitment. Study participants will be referred by their provider, by the OBOT nurse care manager, or they will be self-referred. Referring clinicians will be able to collect verbal consent to share patients' name, email and phone number with study RCs who can reach out to the patient to describe the study in more detail. Referring clinicians will also be able to provide study team contact information to the participant so that they will be able to contact the Research Coordinator (RC) directly. The providers will not be members of the study staff, they are members of the clinical staff who will work with study staff to help make the study available to their patients should their patients find it a good fit.

Following the participant's referral to the study, the RC will conduct a brief phone screen, with the outcomes recorded in a REDCap survey, to determine the participants eligibility. If the participant meets inclusion and exclusion criteria based on the phone screen, then the RC will contact the patient and suggest enrollment in the study followed by study screening. If the participant is deemed ineligible to participate during this screen, their reason for ineligibility will be documented and all pre-screening data will be removed from the pre-screening database.

For patients for whom there are clinical eligibility questions, eligibility will be reviewed by MINDFUL-OBOT Clinical Director, MINDFUL-OBOT PI, or CMC Medical Director prior to the screening visit. The research coordinator will review information provided by the participant during their phone screen to confirm evidence of inclusion criteria. If the patient appears eligible from the brief review, then the Research Coordinator will call all patients with a referral to schedule a screening visit. Eligibility and phone screen information will be stored in a secure REDCap database.

## 6.2.2 Enrollment, Baseline, and/or Randomization

Study enrollment is defined as the date when the informed consent is completed. Once the participant is determined eligible from screening, they will complete their baseline measures. Once baseline measures are completed if they are still eligible, then the participant is ready for randomization, which is described below.

### **Consenting Procedure**

Electronic informed consent will be obtained from each participant at entry into the study via a secure REDCap server hosted at CHA. Informed consent is obtained by the following process:

#### Consent for Participants for study:

**Low-Risk:** The informed consent document will include a full description of the study procedures and associated risks. Because these interventions are well-established with more than 1000 studies demonstrating the safety and efficacy of Mindfulness-based interventions, the groups represent a low-risk experience.

**Consent procedure:** Strict confidentiality during the consenting procedure will be maintained through the use of REDCap for document consent, and the study staff will be trained on maintaining confidentiality during the consent process. The study staff will call or video chat with the participant to guide them through the consenting process. The research coordinator will first describe the measures taken to keep the consent session confidential and safe for the participant, and then will describe the key information of the study verbally, using a study schema diagram designed for easy patient comprehension, and will then give the patient time to review the consent form on their own. The patient will be given a chance to ask questions and express any concerns about the study.

Prior to study enrollment, during the consent process, the participant will be asked to provide their personal information (name, date of birth, address, phone number). No study-specific procedures or investigations will be performed before the patient has signed and dated the Informed Consent Form. The electronically signed and dated informed consent forms will be stored in a secure REDCap server hosted by CHA. The RC will also sign the consent form, indicating that they were present during the consent process. The participant will be emailed a copy of their signed and dated consent form for their own records. Once participant consent has been obtained, the RC will ship a package to the participant containing Oral Fluid Toxicology testing kits.

**Consent assessment:** The participant will also be asked to complete an Informed Consent Assessment via REDCap to ensure comprehension of the study procedures, rights of participants, as well as understanding of the risks and benefits of the study. The participant will not be able to sign the document without having at least 90% correct answers on the consent assessment.

Participants will be given the opportunity to review the study procedures with a trained study staff member if they fail the consent assessment. Participants will also be given an opportunity to correct their answers on the consent assessment. If they can't pass the assessment with at least 90% completely correct answers after reviewing it and the protocol with the coordinator, then they will meet individually with the Research Coordinator or other approved study personnel to be evaluated for the presence of cognitive deficits disrupting their ability to complete study tasks, including completing the MOCA-BLIND to evaluate for cognitive deficits that may prevent them from comprehending the study intervention and study assessments. If participants do not obtain a score of 16 or higher on the MOCA-BLIND, the session will end and they will be permitted to reschedule to take the MOCA-BLIND once more on a different day. If they do not obtain a score of 16 or higher on the second day, they will not be permitted to join the study. Since participants with opioid use disorder often have transient mental health symptoms or intoxication related to recent substance use, participants with transient symptoms related to recent substance use may be able to wait for a re-review of eligibility after 30 days based on the judgement of the Principal Investigator.

Participants with at least one score of 90% or higher on the Informed Consent assessment AND a score of 16 or higher on the MOCA-BLIND within up to two screening visits will be eligible for participation in the study. Once the participant demonstrates understanding of the study and agrees to participate in the study, the consent will be signed in the presence of the research coordinator or another trained member of the study team staff. After completion, participants will be given an additional copy of the signed informed consent form for their own records.

Consented patients will be assigned a numeric study number based on their order of enrollment and study acrostic which is based on letters (to allow for cross-referencing and prevent mistaken confusion among participants if a digit is incorrect), and will complete the screening and baseline assessment battery, which will take place after informed consent.

## **Screening Assessments (Consent and Screening Visit)**

After participant consent has been obtained, the research coordinator will provide the participant with a secure REDCap link to the PROMIS-ASF, and PhenX toolkit surveys, as well as a secure link to a screening CAT-MH survey, to evaluate for eligibility prior to proceeding with baseline assessments. The RC will also supervise an oral fluid test with the participant to assess for substance use. If the screening process suggests that the participant meets exclusion criteria or brings up other questions about eligibility, then the RC will contact the PI or clinical director to review the information and decide prior to proceeding to baseline assessments. If a participant's PROMIS-ASF T score is greater than 55 (Raw > 16), then the participant will be determined to have an anxiety disorder even if it was not previously diagnosed clinically.

Since participants with opioid use disorder often have transient mental health symptoms or intoxication related to recent substance use, participants with transient symptoms related to recent substance use may be able to wait for a re-review of eligibility after 30 days.

During this screening visit, all eligible participants will be asked to fill out a Scheduling Acceptability form to rate the level of acceptability of the available study group day and time for both M-ROCC and control group times at the site, asking on a 0-10 scale how much they will be able to attend the group times.

## **Baseline Assessments (Baseline Visit)**

### Baseline Survey Session and Computer Tasks Visit:

Eligible participants will complete baseline surveys through a link to the secure REDCap database. They will receive a password protected survey link through an email from the study team.

All participants will be shipped a package containing sponge-based testing kits for Oral Fluid Toxicology testing. Oral fluid toxicology tests will be conducted via videochat with a research coordinator to ensure proper collection. The participant will hold the results panel of the test up to their camera for the research coordinator to screenshot using the HIPAA compliant screenshotting tool "Droplr". These screenshots will be stored in Droplr's secure cloud server before being transferred to the secure CHA Google Drive. Participant faces and other PHI will not be included in the screenshot.

The Baseline Survey Session is expected to take approximately 1.5 hours. Please refer to schedule of evaluations (Section 6.1) for an exact list of assessments used in this session.

### **Randomization**

We will randomize participants in a 1:1 ratio of M-ROCC arm to control arm. We will randomize participants in randomly selected blocks of 4, 6, or 8 in a 1:1 ratio.

Randomization will be conducted as follows:

- 1) Participants who complete baseline measures and have a scheduling acceptability form will be entered into the randomization database.
- 2) Upon final review of eligibility, eligible participants will be marked as ready for randomization in the study database, which will alert the data analyst by automated email generated by REDCap.
- 3) The data analyst will randomize participants who are ready using a randomly selected block size (4, 6 or 8) (1:M-ROCC; 1:Control) and will enter the randomization status into the Study Status spreadsheet which the research coordinators will have access to and is kept secure within the CHA G Suite system.
- 4) The research coordinator will call the participant by phone to let them know the date/time that they can start LDM/Control.

### Participant De-identification, Randomization, Allotment, and Blinding:

Upon consenting to the study, each participant will be assigned a study number by the research coordinator. Randomization will occur using the assigned study number, which the Data Analyst will use to enter each participant into the randomization spreadsheet. The Data Analyst will be blinded to participant identity prior to and during randomization. The research coordinator will not have access to the randomization spreadsheet.

#### 6.2.3 Blinding

See Table 2 for blinding status for study staff. Participants will not be blinded to their assigned study arm (M-ROCC vs. control), nor will the research coordinators, data analyst, or methodologists. The PI will be blinded to assigned study arm when reviewing data quality, adverse events, protocol violations, etc.

Table 2. Blinding Status of Study Staff

Study Role	Blinding Status	Time of unblinding
------------	-----------------	--------------------

PI	Blinded	When all primary outcome data have been collected and when database is locked
Data Analyst ([name], [name], [name])	Not Blinded	Will prepare reports for DSMB with unblinded data, but will not have contact with participants.
Methodologists ([name]/[name])	Not Blinded	Will review reports for DSMB with unblinded data, but will not have contact with participants.
RCs	Not blinded	
Clinical/Medical Directors	Not blinded	
Participants	Not blinded	

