### **3. Increased anxiety due to difficulties in mental training program**

Mindfulness practices can sometimes cause anxiety for those who practice. Support from the Group Leader and the group can help participants recognize that this anxiety is part of the process and can help people learn to manage these feelings. If meditation and mental exercises are causing a worsening of anxiety for participants, they will be encouraged within groups to change their approach to the practice. Research coordinators will assess for worsening symptoms every two weeks during the engagement call adverse events report, and also during each live-online group session. If the participant(s) are unable to find a way to practice without eliciting an increase in symptoms, then they may be asked to stop practicing and to meet with either the M-ROCC Clinical Director, the CMC Medical Director, or the Principal Investigator for an evaluation. The participant may ultimately be terminated from the study if they are experiencing an adverse reaction. These participants may continue to receive other treatments at their primary care site as part of their ongoing treatment plan.

- 4. In some very rare cases, meditation practice can lead to a dissociative state or to psychosis.** This is more likely in participants with current conditions of or a predisposition to psychosis. Participants experiencing active psychosis are excluded from participating in this study. If a participant begins to experience these feelings during his or her time in the study, then the study staff and care team will work together to alert the appropriate care team providers and study investigators immediately. The participant may be asked to stop practicing and to meet with either the CMC Medical Director or the Principal Investigator for an evaluation in person or via videoconference while a member of the study staff is onsite with the person. Videoconferencing will occur through the HIPAA compliant and encrypted communications platform zoom. The participant may ultimately be terminated from the study if he or she is experiencing an adverse reaction. These participants may continue to receive other treatments at their primary care site as part of their ongoing treatment plan. If the participant experiences a dissociative state or psychosis during a group session, the research coordinator and/or group leader will ask the participant to meet with them

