## **8. INTERVENTION DISCONTINUATION**

### Participant Withdrawal/Termination Criteria:

#### *Withdrawal/Termination criteria for Participants:*

Participants may be discontinued from just the study intervention (“Group Discontinuation”) OR both the study intervention and study assessments (“Study Withdrawal”) at any time.

Specific reasons for discontinuing a participant (“Group Discontinuation”) from the group are:

1. Voluntary discontinuation by the participant who is at any time free to discontinue his or her participation in the group, without prejudice to further treatment.
2. Safety reasons as judged by the investigator.
3. Substance use disorder or psychiatric symptoms worsen to a level that requires a higher level of care.
4. Revealing private information about other participants in the groups.

Specific reasons for withdrawing a participant (“Study Withdrawal”) from the entire study are:

1. Voluntary discontinuation by the participant who is at any time free to discontinue his or her participation in the study, without prejudice to further treatment.
2. Safety reasons as judged by the investigator.
3. Incorrect enrollment (i.e., the participant does not meet the required inclusion/exclusion criteria) of the participant.
4. Active severe substance use disorder or level of intoxication during study procedures that precludes ability to conduct assessments.

5. Participants unable to complete baseline assessments.

Participants who discontinue will be asked about the reason(s) for their discontinuation and the presence of any adverse events. If possible, they will be seen and assessed by the Principal Investigator. Serious and Unexpected Adverse events will be followed up.

If participants are terminated from group intervention for any reason (except incorrect enrollment or safety concerns that endanger the study team), then they will still be expected to complete their outcome assessments, unless the participant revokes informed consent and withdraws from study.

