Safety precautions for discontinuing a participant will be followed. Participants will be informed about discontinuation from group by the clinician leading the group and alternative treatment options will be discussed with the participant. If the participant is not available to receive this communication, then a letter will be sent informing the participant about the group discontinuation and providing alternative treatment options. Decisions about group intervention discontinuation will be made by the PI and group leaders but will be discussed with the CMC Medical Director for consultation prior to providing a group discontinuation letter.

If a participant is withdrawn from the study, they will be contacted by the Principal Investigator and informed the reason they are being withdrawn. A Withdrawal Letter will be sent informing the participant about the study withdrawal. If the participant was still in a study group, then the group discontinuation process will also be completed as described above with attention to providing alternative treatment options.

Participation in this research study is voluntary. Participants can choose not to participate, and their decision will in no way affect the quality of care they receive at their site or their working relationship with their site. Participants may elect at any point to discontinue their participation in this study.

Participants who become pregnant during the study will not be discontinued. The current standard of care for women with opioid use disorder is to be maintained on medication-assisted treatment with methadone or buprenorphine during the pregnancy. In fact, buprenorphine treatment leads to shorter duration of neonatal abstinence syndrome than methadone, leading buprenorphine to be the gold standard for treatment during pregnancy. To reduce risk of fetal exposure to naloxone, the current standard is for pregnant participants to be maintained on

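### The PI is listed as blinded to arm until database lock, but the PI's own duties will reveal the arm of at least some participants before then

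*Combined protocol and SAP*

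**What the plan says.** Section 6.2.3 states: "The PI will be blinded to assigned study arm when reviewing data quality, adverse events, protocol violations, etc". Table 2 gives the PI's time of unblinding as "When all primary outcome data have been collected and when database is locked". The PI is the only role in that table listed as blinded. Participants, research coordinators, data analysts, methodologists and the clinical and medical directors are all listed as not blinded.

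Other sections give the PI work with individual participants:

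- Section 8: "Decisions about group intervention discontinuation will be made by the PI and group leaders", with the CMC Medical Director consulted. Of participants who discontinue, it says "If possible, they will be seen and assessed by the Principal Investigator". The PI also contacts each participant withdrawn from the study to give the reason.
- Section 7.2.1, item 3: a participant whose symptoms rise with practice may be asked to stop and "to meet with either the M-ROCC Clinical Director, the CMC Medical Director, or the Principal Investigator for an evaluation". Item 4 names the CMC Medical Director or the PI for dissociation or psychosis.
- Section 7.5: the PI is told of every adverse event within 48 hours and decides what to do. The CMC Medical Director and/or the PI then consider whether the participant leaves the intervention or the study.
- Section 5.4: "Data on adherence to the intervention protocol will be collected weekly by research staff and reviewed monthly by the PI", and "Adherence of participants will be evaluated by attendance at weekly sessions (Control, LDM, MCS or MTPC-OD").

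Section 10.3.5 restricts study report tables to data pooled over arms and keeps the closed safety report from the PI.

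**The concern.** A person cannot be blind to assignment and also take part in decisions that turn on it. Deciding with a participant's group leaders whether that person leaves the group shows which group it is. Judging a reaction to meditation practice points to M-ROCC. The plan neither masks the arm in these duties nor provides for the PI to be unblinded case by case.

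At stake are the judgements the PI makes: action after an adverse event, the basis for calling a problem related to the research (Section 7.4), group discontinuation, and review of deviations. In a trial where every other listed role knows the arm, a report that the PI reviewed these matters masked would carry weight. The plan as written does not support that statement.

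**Working it through.** The plan states no figure on this point, so the check sets the blinding statement against each duty and then sizes the one route that can be counted.

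**Duty by duty**

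| PI duty | Section | Does it show the arm? | Is someone else named? |
|---|---|---|---|
| Decide group discontinuation with group leaders | 8 | Yes in practice: leaders are described separately by arm (10.3.1) and the decision concerns a specific group | No; Medical Director consulted only |
| See participants who discontinue, if possible | 8 | Likely: participants know their arm and nothing asks them to conceal it | No |
| Contact withdrawn participants | 8 | Possibly, in conversation | No |
| Evaluate reactions to meditation | 7.2.1, items 3 and 4 | Ordinarily points to M-ROCC | Yes: one of three (anxiety) or one of two (dissociation, psychosis) |
| Decide action after adverse events | 7.5 | Likely where leaving the intervention is considered | Partly: decision about study status shared with Medical Director |
| Review adherence | 5.4, Table 3 | Only if session type or the arm's threshold is shown | Not applicable |

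The first row is enough for the conclusion. Group discontinuation happens during the 24 weeks, so it precedes the unblinding point in Table 2.

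**Size of the discontinuation route**

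Inputs from Section 9.2: 96 per arm, 192 in total; anticipated dropout from intervention at 24 weeks of 17-28% in M-ROCC and 21-44% in control.

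- Low end: 0.17 × 96 + 0.21 × 96 = 16.3 + 20.2 = 36.5; 36.5 / 192 = 19%.
- High end: 0.28 × 96 + 0.44 × 96 = 26.9 + 42.2 = 69.1; 69.1 / 192 = 36%.

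This is a ceiling of about 36 to 69 participants, for two reasons. The PI sees those who discontinue only where possible, and someone who leaves voluntarily needs no PI decision. It also assumes that dropout in Section 9.2 means leaving the group. Section 9.5.2 defines intervention retention by an active buprenorphine prescription, so the ranges may describe something else.

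**Adherence review**

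Section 5.4 scores each session 0, 1 or 2 (absent, completed, incomplete) and lists the session types that count. It does not say that the PI receives session type by participant. The thresholds do differ by arm: "Participants will be considered adherent to the control intervention if they complete 15/24 control groups", against at least 3 LDM plus at least 12 MTPC-OD or MCS sessions for M-ROCC. A report showing the threshold applied would therefore reveal the arm. The frequency is also inconsistent: monthly PI review in Section 5.4, twice-yearly in Table 3. The monthly sentence stands under the subheading on group leader adherence, although the text that follows concerns participants' attendance. Exposure by this route cannot be sized from the documents.

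**The case against.** The best defence is that Section 6.2.3 limits the PI's blinding to certain review tasks, and that Section 10.3.5 supports it: pooled tables, and a closed safety report the PI does not see. Knowing some individuals' arms does not give the PI results by arm. This stands, and the PI's blinding to by-arm summaries survives. It does not rescue the rest. Adverse event review is one of the tasks named, Table 2 carries no task limit, and pooled tables do not hide assignments learned case by case.

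The defence is also right that the consequence is bounded. The primary outcome rests on oral fluid tests recorded by coordinators and on self-report, not on PI judgement. Participants removed from the group are, with few exceptions, still expected to complete outcome assessments (Section 8), and the analysis is by intention to treat. The Senior Research Coordinator and Clinical Director also review adverse events weekly (Section 7).

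A reader might infer three stronger things that the documents do not support:

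- That there is no PI blinding at all. Section 10.3.5 shows otherwise for by-arm safety data.
- That adherence review reveals all 192 participants at its first monthly round. The report format is not given, and about 24 are randomised each month (Section 9.2), so one early review could cover only about one cohort.
- That 36 to 69 participants will be assessed or decided on by the PI. That range is only a ceiling.

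**Conclusion.** The point holds at participant level. Section 6.2.3 and Table 2 state a blinding that Sections 7.2.1, 7.5 and 8 defeat for at least some participants before lock. The conclusion needs only that some group discontinuations reach the PI as Section 8 directs and that the arm is not masked there; no section masks it. By the discontinuation route the ceiling is about 36 to 69 of 192 (19% to 36%), if dropout in Section 9.2 means leaving the group. Exposure through adherence review is unknown.

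The likely effect on the primary outcome is small. The exposure lies in adverse event handling, discontinuation and deviation review, and in what the trial may later say about masking them.

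**What to change.** 1. Reword Section 6.2.3 and Table 2: the PI is not blinded to individual assignment, and is blinded only to by-arm aggregate data until primary outcome data are complete and the database is locked.
2. Do not describe PI review of adverse events, deviations or withdrawals as masked, in the protocol or in reports.
3. Give the PI adherence as attended or not attended, without session type or the arm-specific threshold. Otherwise the PI could tabulate attendance by arm, which would undo the blinding kept under item 1.
4. Reconcile Sections 5.4, 6.2.3, 7.2.1, 7.5 and 8 and Table 3 with the new wording, including the monthly versus twice-yearly adherence review.

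This leaves clinical evaluation and discontinuation decisions where the protocol puts them. The cost is a wording amendment and a change to the layout of one report.
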